3.7 Timing of outcome assessments
Outcome assessment
Time points at which the outcomes are measured including visit “windows”

4. Statistical Principles

4.1 Confidence intervals and *P* values

An overall significance level of 0.05 is used for the composite primary endpoints and are tested in the specified order as seen in section 3.3, above. To control the overall significance level pertaining to the primary hypotheses, the fallback method for alpha spending is used for the statistical analyses of relative risk comparing the two randomisation groups, Cod liver oil and Corn oil. If the first analysis results in significant results, i.e., $p \leq 0.018$, according to section 3.3, the second null-hypothesis can be tested at a significance level of $0.018 + 0.030 = 0.048$. If the first null hypothesis is not rejected, the second is tested at the stated significance level of 0.03. Each following null hypothesis to be tested has a significance level of its stated level plus the sum of the levels of previous tests that result in a significant result. Supplementary analyses, such as regression analyses, will not be part of the fallback method, as these are expected to be highly correlated to the primary analyses. Confidence interval and p-values will be provided for all variables tested statistically.

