3.3 Sample size

The fallback method (<https://www.fda.gov/media/102657/download>) will be used to correct for testing of multiple primary endpoints.

The total alpha (0.05) will be divided among the endpoints, and a fixed sequence for the testing will be maintained. As the testing sequence progresses, a successful test preserves its assigned alpha as "saved" (unused) alpha that is passed along to the next

test in the sequence. This passed-along alpha is added to the assigned alpha of the next endpoint, and the summed alpha is used for testing that endpoint. Thus, as sequential tests are successful, the alpha accumulates for the endpoints later in the sequence; these endpoints are then tested with progressively larger alphas.

Endpoints in testing order with power calculation:

1. Serious COVID-19 (MSIS-confirmed COVID-19 with dyspnoea, hospitalization, or death). (MSIS: Mandatory Norwegian Surveillance System for Communicable Diseases). Assigned $\alpha=0.018$.

Based on the observations in Koronastudien of a 40% reduction in serious COVID-19 in the group reporting use of cod liver oil, and an expected incidence of 0.25%, a power of 70%, 67,000 participants will have to be included for this endpoint.

2. COVID-19 positive PCR (MSIS). Assigned $\alpha=0.03$.

Based on the observations in Koronastudien of a 20% reduction in COVID-19 incidence in the group reporting use of cod liver oil, and an expected incidence of 1%, a power of 70%, 65,000 participants will have to be included for this endpoint.

3. A negative SARS-CoV-2 test (MSIS). Assigned $\alpha=0.001$.

COVID tests (SARS-CoV2-2), real time (RT)-PCR, are mostly obtained because of a suspicion of COVID-19. The number of negative COVID tests from one week after starting taking cod liver oil/placebo and to the end of the intervention period. This endpoint has been added as an alternative to the Positive PCR or bacterial culture endpoint (now a secondary endpoint, as it is not available at this time).

4. Self-reported airway infection. Assigned $\alpha=0.001$.

Based on the expected frequency of airway infections in Koronastudien of >30% and as a threshold of clinically interesting reduction of all airway infections of 10%, 23,000 participants will have to be included for this endpoint. The study has a power for this endpoint >95%. 16,000 participants in the study will give an 80% power for this endpoint.

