The handling data will be closely connected to the handling of data in Koronastudien, and for data handling purposes, the CLOC study will be treated as a sub-study of Koronastudien. An application to process and store data from the two studies together will be sent to the Data Protection Officer at Oslo University Hospital. Koronastudien has been approved by the Data Protection Officer at Oslo University Hospital in accordance with the European GDPR regulations.

The University of Oslo service for sensitive data (TSD) will be used to collect, store, and analyze data. Additionally, HUNT cloud and LEDIDI Prjcts will be used for analyzing data. The data will be analyzed without any directly personally identifying information using a Study ID instead. The patient list connecting the patient identity with the study ID will be kept in a separate folder in TSD, and the backup will be kept at an encrypted USB data storage device. Deidentified data will be backed up at K:/sensitive, a secure location at the Oslo University Hospital's internal web.

9. Statistical considerations

The detailed statistical analysis plan will be approved by the study steering committee before unblinding.

Statistical Hypotheses

See Sample Size Determination and the statistical analysis plan

Sample Size Determination

The fallback method (https://www.fda.gov/media/102657/download) will be used to correct for testing of multiple primary endpoints.

The total alpha (0.05) will be divided among the endpoints, and a fixed sequence for the testing will be maintained. As the testing sequence progresses, a successful test preserves its assigned alpha as "saved" (unused) alpha that is passed along to the next test in the sequence. This passed-along alpha is added to the assigned alpha of the next endpoint, and the summed alpha is used for testing that endpoint. Thus, as sequential tests are successful, the alpha accumulates for the endpoints later in the sequence; these endpoints are then tested with progressively larger alphas.

Endpoints in testing order with power calculation:

1. Serious Covid-19 (Covid-19 with self-reported dyspnea, self-reported hospitalization, or death). Assigned α =0.018.

Based on the observations in Koronastudien of a 40% reduction in serious Covid-19 in the group reporting use of cod liver oil, and an expected incidence of 0.25%, a power of 70%, 67,000 participants will have to be included for this endpoint.

- Covid-19 positive PCR. Assigned α=0.03.

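### SAP 4.1 passes alpha differently from SAP 3.3 and the protocol; followed literally it does not hold the family-wise error at 0.05

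*SAP*

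**What the plan says.** Four primary endpoints are tested in fixed order: serious COVID-19 (H1), positive PCR (H2), negative SARS-CoV-2 tests (H3) and self-reported airway infection (H4). Their assigned alphas are 0.018, 0.03, 0.001 and 0.001.

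SAP 3.3 describes what happens to the alpha of a successful test: "This passed-along alpha is added to the assigned alpha of the next endpoint, and the summed alpha is used for testing that endpoint". Protocol section 9 (Sample Size Determination) says the same, describing saved alpha "that is passed along to the next test in the sequence".

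SAP 4.1 claims overall control: "An overall significance level of 0.05 is used for the composite primary endpoints". It names the method: "the fallback method for alpha spending is used for the statistical analyses of relative risk". Its worked example stops at H2, which is tested at 0.048 if H1 succeeds and at 0.03 otherwise. For every later hypothesis it then gives a general rule: "its stated level plus the sum of the levels of previous tests that result in a significant result".

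**The concern.** In the fallback method a failed test breaks the chain: alpha saved earlier is not carried past it. The general rule in 4.1 has no such break. It adds the levels of all earlier successes, so the same alpha can be spent on H3, lost there, and spent again on H4.

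Two things are at stake. First, an analyst who follows 4.1 and one who follows 3.3 can reach opposite conclusions on a primary endpoint from the same p-value, for example 0.01. Second, the 0.05 control that 4.1 claims may fail in the situation the trial was powered for, a real effect on H1 or H2.

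**Working it through.** **Inputs.** Assigned alphas 0.018, 0.03, 0.001 and 0.001 (SAP 3.3, protocol section 9); they sum to 0.05. Planned power is 70% for H1 and for H2 (SAP 3.3). Sidedness is not stated; two-sided tests are assumed because they reproduce the planned sample sizes.

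**The plan's own figures.** Total N = 2 × [z(1−α/2)·√(2p̄(1−p̄)) + z(0.70)·√(p₁(1−p₁) + p₂(1−p₂))]² / (p₁−p₂)².
- H1: p₁ = 0.0025, p₂ = 0.0015, α = 0.018 gives 66,684 (stated 67,000).
- H2: p₁ = 0.010, p₂ = 0.008, α = 0.03 gives 64,754 (stated 65,000).

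Both reproduce, so 70% is a fair planning value. If H1 succeeds, H2 is tested at 0.048 and its power is Φ(z(0.985) + z(0.70) − z(0.976)) = 0.763.

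**Where the rules differ.** H1 and H2 have the same levels under both rules. The five differences are:

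| Situation | Endpoint | 4.1 | 3.3 / protocol |
|---|---|---|---|
| H1 rejected, H2 not | H3 | 0.019 | 0.001 |
| H1 and H2 rejected, H3 not | H4 | 0.049 | 0.001 |
| Only H2 rejected | H4 | 0.031 | 0.001 |
| Only H1 rejected | H4 | 0.019 | 0.001 |
| H1 and H3 rejected, H2 not | H4 | 0.020 | 0.002 |

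**Family-wise error with H1 and H2 effective, H3 and H4 null, independent tests.** The probabilities of the H1/H2 results at planned power are:
- both rejected: 0.70 × 0.763 = 0.534
- H1 only: 0.70 × 0.237 = 0.166
- H2 only: 0.30 × 0.70 = 0.210
- neither: 0.30 × 0.30 = 0.090

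The chance of at least one false rejection among H3 and H4 in each case is:

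| H1/H2 result | 4.1 | Fallback |
|---|---|---|
| Both | 1 − 0.951² = 0.0956 | 1 − 0.951 × 0.999 = 0.0500 |
| H1 only | 1 − 0.981² = 0.0376 | 1 − 0.999² = 0.0020 |
| H2 only | 1 − 0.969² = 0.0610 | 1 − 0.969 × 0.999 = 0.0320 |
| Neither | 1 − 0.999² = 0.0020 | 0.0020 |

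The weighted sums are:
- 4.1: 0.0511 + 0.0062 + 0.0128 + 0.0002 = **0.0703**.
- Fallback: 0.0267 + 0.0003 + 0.0067 + 0.0002 = **0.0339**.

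As power approaches 1 only the first row remains: 0.0956 against 0.0500.

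**Other configurations under 4.1.**
- H2, H3 and H4 null: 0.70 × (1 − 0.952 × 0.981²) + 0.30 × (1 − 0.970 × 0.999²) = 0.0683; 0.0838 at power 1.
- H1, H3 and H4 null: 0.018 + 0.982 × (0.70 × 0.0610 + 0.30 × 0.0020) = 0.0605; 0.0779 at power 1.
- At power 1, H2 and H4 null: 1 − 0.952 × 0.980 = 0.0670. H2 and H3 null: 1 − 0.952 × 0.981 = 0.0661.
- Global null: 1 − 0.982 × 0.970 × 0.999² = 0.0494 under both rules.

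These five are the only ones of the 15 configurations containing a true null in which 4.1 exceeds 0.05. Fallback never does.

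**How often the rules diverge (H3 and H4 null, planned power).** Levels differ with probability 0.166 + 0.534 × 0.951 + 0.210 × 0.969 = 0.877. The significance decision differs far less often, in about 3.6% of trials, matching the gap between 7.03% and 3.39%.

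**Correlation.** Serious COVID-19 is a subset of COVID-19, so the planned incidences imply an H1–H2 correlation of √(0.0025 × 0.99 / (0.01 × 0.9975)) = 0.498. The documents give no other correlations. With H1–H2 at 0.5, H3 and H4 null, and all other correlations assumed to be 0, 0.3 or 0.5, simulation gives 7.0%, 6.4% or 5.5% at planned power, and 9.5%, 9.3% or 8.9% as power approaches 1.

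**The case against.** The best reply is that 4.1 is loose drafting, not a different method. It names the fallback method, refers back to 3.3, and gives an H2 example that agrees; 3.3 itself never states outright what happens when an intermediate test fails. Loose drafting is the likely explanation. It does not settle the matter, because the example stops where the rules coincide and the sentence that follows is the only instruction in 4.1 for H3 and H4. The sentence also has a worse reading. If levels means those actually used rather than assigned, H3 would be tested at 0.018 + 0.048 + 0.001 = 0.067 after two successes, above the total alpha, and the 7.0% becomes 8.8%.

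Second, the size depends on the scenario.
- Ten of the 15 configurations show no inflation.
- With H1 and H2 at only 30% power the literal rule gives 3.2%, and the plan itself warns that low COVID-19 incidence could cut power.
- Negative tests and airway infections may well be correlated: correlating H3 and H4 alone at 0.5, 0.7 or 0.9 gives 6.6%, 6.0% or 5.1% at planned power.
- SAP Appendix 1 restricts the serious-disease analysis to participants who meet the second primary. On that reading H1 compares about 25% of 335 with 18.75% of 268, its power falls to about 29%, the nesting correlation no longer applies, and the error is about 5.5%.

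All of this stands as a limit on the excess. None of it restores the 0.05 claim, which should hold whichever endpoints respond and should not rest on low power or on correlations the plan does not give.

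**Conclusion.** The concern holds. SAP 4.1 conflicts with SAP 3.3 and the protocol on the levels for H3 and H4, and the literal 4.1 rule does not control the family-wise error at 0.05. With H1 and H2 effective at planned power, H3 and H4 null and independent two-sided tests, the error is 7.0% against 3.4% under fallback. The maximum under independence is 9.6%, and the bound under any dependence is 0.049 + 0.049 = 9.8%. The excess needs a true effect on H1 or H2 and at least two true nulls later in the sequence, and it is modest at planned power if the tests are clearly correlated. Because one p-value can yield opposite primary conclusions depending on the section followed, this must be fixed before unblinding.

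**What to change.** Replace the last rule in SAP 4.1 with: each hypothesis is tested at its assigned alpha plus the level at which the immediately preceding hypothesis was tested, if that hypothesis was rejected; otherwise at its assigned alpha alone. Add the resulting levels:

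| Endpoint | Level |
|---|---|
| H1 | 0.018 |
| H2 | 0.048 if H1 rejected; otherwise 0.030 |
| H3 | 0.049 if H1 and H2 rejected; 0.031 if only H2 rejected; 0.001 if H2 not rejected |
| H4 | 0.050, 0.032 or 0.002 if H3 was rejected at 0.049, 0.031 or 0.001; otherwise 0.001 |

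This brings 4.1 into line with 3.3 and the protocol and restores control at 0.05. It costs one paragraph and a small table. It needs no new data and leaves the assigned alphas, testing order and sample size unchanged. Relative to 4.1 with assigned levels, thresholds become stricter only in the five situations listed above.

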4.2 Adherence and protocol deviations

The Intention-to-treat (ITT) population will be used for statistical testing of the primary variables. Hence, anyone who received bottles of cod liver/corn oil will participate in the primary variables' analyses. As a number of bottle shipments were for several reasons returned to sender, such as wrong address, address in another country or did not collect the bottles at the post office despite several urgings, the ITT population is defined as those who had the choice to start taking cod liver/corn oil. Primary variable statistics will also be presented for all who were sent cod liver/corn oils. Participants with missing data on primary variables will be considered as having a negative outcome. Supplementary analyses will be conducted on participants who have reported on the primary variables and on taking oil at given fractions, to be specified when analysing the data, of “the last fortnight”.

5. Trial Population

5.1 Screening data

Data from the first reported questionnaire will be considered as baseline wherever such values are considered necessary.

5.2 Eligibility

All participants invited to this study are considered eligible.

- 5.3 Recruitment
Information to be included in the CONSORT flow diagram.
- 5.4 Withdrawal/follow-up
The level of reported oil consumption per time unit and overall will be presented. The number of participants with last reported data will be presented for each data collection time-point.
- 5.5 Baseline patient characteristics
The following baseline variables² will be presented for each treatment group and overall:

- Age group
- Gender
- Weight
- Height
- BMI
- Occupational status
- Education level
- Household income
- Household count
- Children living at home
- Smoking habits
- Chronic disease (Yes/No)
- Parents ethnic origin
- Skin type
- Sun exposure (July to October 2020)
- Dietary intake:
 - Vitamin D supplement
 - Omega-3 supplement
 - Cod liver oil
 - Fatty fish intake

Follow-up variables:

- Compliance
- Airways infections
- SARS-CoV-2-tested (negative and positive)
- Dyspnoea (among COVID positive participants)
- Side effects (counts (%)), self-reported free-text fields

Lab

- Vitamin D (baseline and change from baseline)
- Omega-3 index (baseline and change from baseline)
- Baseline serology

MSIS data:

- Positive and negative test results

² The specific SAS variable names in the received data set are presented in Appendix 1.

For continuous baseline variables N, mean, standard deviation, median, minima and maxima will be presented. For categorical variables, N and Per cent will be presented for each oil group.

6. Analysis

6.1 Outcome definitions

Primary variables:

- First primary: Serious COVID-19 (MSIS-confirmed COVID-19 with dyspnoea, hospitalisation, or death)
- Second primary: COVID-19 defined by positive PCR obtained from MSIS
- Third primary: A negative SARS-CoV-2 test (MSIS).
- Fourth primary: Self-reported airways infection

The first incidence of report of any of the above primary variables will be used in the analyses. The specified order will be used for the fallback analyses. The values of all variables will be Yes/No to the condition together with time from one week after start of oil consumption to first reporting of the condition, i.e. Yes (except for third primary variable, where total number of negative tests is reported). Those not reporting a Yes answer, the last reported time will be used as censoring time. The date from one week after oil-consumption starts to the date of reporting of a Yes will be converted to number of days from the first to the second date.

The primary analysis set is the defined ITT sample with missing data on outcome counting as the negative outcome.

Compliance

For sensitivity analyses on compliance, we will define compliant participants as those having taken CLO for at least 2 months. We will also analyse participants based on volume CLO taken (more than 250 ml).

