 - NA = has not filled out form

- Death criteria

- Participant registered as dead/deceased in the National Population Register after a positive cov test (MSIS), but only if the death was related to COVID-19 based on hospital records or information from relatives.

- **Second primary:** New MSIS positive

- *CLOC_primary_2_msis_status*
 - Created from *MSIS_CLOC_test_status*
 - 1 = tested positive for the first time during **CLOC participation period**
 - 2 = only tested negative during **CLOC participation period** (never positive)
 - 3 = untested during **CLOC participation period** (never positive)
- Participants who have tested positive within one week after start of oil consumption are excluded from the analysis (*exclude_Msis_transtart7d*).
- MSIS criteria
 - Variable: *MSIS_CLOC_test_status*
 - 1 = tested positive for the first time during CLOC
 - 2 = only tested neg during CLOC (never positive)
 - *Variables obtained through MSIS (translated): “Test date” and “Test result”*
 - Variable to be analyzed as second primary endpoint identifying only tests registered during the **CLOC participation period** (defined as period from start of cod liver oil/placebo consumption (*deriv_Date_CLO_start_corr*) to June 2, 2021).
- **Third primary: Negative test**
 - *CLOC_primary_3_negative_tests*
 - Generated from *MSIS_CLOC_TotalTests_7d_neg*
 - Sum of total negative tests registered during the period from one week after start of cod liver oil/placebo consumption (*deriv_Date_CLO_start_corr*) to June 2, 2021.
 - 0 if no tests registered
 - Negative test criteria
 - Variable: *MSIS_CLOC_TotalTests_7d_neg*
 - Sum of total negative tests registered during the period from one week after start of cod liver oil/placebo consumption (*deriv_Date_CLO_start_corr*) to June 2, 2021.
 - Supplementary variables
 - *MSIS_CLOC_FirstNegative*
 - Date of first negative test registered during the **CLOC participation period**.
 - *MSIS_CLOC_LastNegative*
 - Date of last negative test registered during the **CLOC participation period**.
- **Forth primary: Self-reported airway infections**
 - *CLOC_primary_4_selfrep_airway*
 - Generated from *deriv_respinf_date_yn*
 - 1 = ever answered yes and provided valid date in any form
 - 0 = only answered no, or provided non-valid date in any form
 - 999 = has filled out form, has not answered airway infections question
 - NA = has not filled out form

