In rare instances, it may be necessary for a participant to permanently discontinue study intervention. If study intervention is permanently discontinued, the participant will remain in the study to be evaluated for relevant endpoints unless the participants want to also withdraw.

Participant Discontinuation/Withdrawal from the Study

A participant may withdraw from the study at any time at his/her own request or may be withdrawn at any time at the discretion of the investigator for safety, behavioral, or compliance reasons.

The participant will be permanently discontinued both from the study intervention and from the study at that time.

The participant may also withdraw the consent to use some of his or her data as described in the consent form.

Lost to Follow Up

A participant will be considered lost to follow-up if he or she repeatedly fails to return for scheduled visits and is unable to be contacted by the study and data on registries are no longer recorded (this will mostly be participants moving abroad).

Cod Liver Oil for Covid-19 Prevention Study, protocol version 1.2, November 10, 2021

8. Study Assessments and Procedures

Endpoint Ascertainment and Validation

Se also definition of endpoints in chapter 3.

Endpoint ascertainment will be done by obtaining endpoint data from relevant registries. The connection between the CLOC study and the registries will be made by the Norwegian Personal Identity Number (PIN), which ensures unambiguous identification of every subject. The PIN number is validated by 2-factor authentication when the informed consent is signed electronically.

Registry data will be compared to the self-reported symptoms. In cases where an episode of respiratory illness evidenced by a positive PCR or culture is not accompanied by a symptom report form, the patient will be encouraged to complete a symptom form.

Diagnoses in hospitalized patients and outpatient visits are reported to the Norwegian Patient Registry (NPR), while deaths are reported to the Causes of Death Registry.

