 Based on the observations in Koronastudien of a 20% reduction in Covid-19 incidence in the group reporting use of cod liver oil, and an expected incidence of 1%, a power of 70%, 65,000 participants will have to be included for this endpoint.
- Frequency of negative SARS-CoV-2 tests (MSIS). Assigned α=0.001. Covid tests (SARS-CoV2-2), real time (RT)-PCR, are mostly obtained because of a suspicion of COVID-19. The number of negative covid tests from one week after starting taking cod liver oil/placebo and to the end of the intervention period. This endpoint has been added as an alternative to the Positive PCR or bacterial culture endpoint (secondary endpoint, which is not available at this time).
- 4. Self-reported airway infection (yes/no). Assigned α =0.001. Based on the expected frequency of airway infections in Koronastudien of >30% and as a threshold of clinically interesting reduction of all airway infections of 10%, 23,000 participants will have to be included for this endpoint. The study has a power for this endpoint >95%. 16000 participants in the study will give an 80% power for this endpoint.

Analysis sets

Participants will be assigned to the cod liver oil or placebo group in a 1:1 ratio. The primary endpoints will be calculated using relative risks, Kaplan-Meier plots and Cox regression on the intention to treat (ITT) population with missing data on outcome counting as the negative outcome.

Compliance with cod liver oil taking and power of the study

The power calculation is based on data from Koronastudien and participants reporting taking cod liver oil. We have no data on how often cod liver oil was used by these participants but believe that it is less than once daily on average. Thus, although many participants in the CLOC study will not be fully compliant, we expect that a large majority of participants will have the same level of cod liver oil taking as found in Koronastudien. However, to increase the power, we will attempt to recruit up to 80.000 participants to increase the power of the study.

Interim Analyses

Covid-19-prevalence and power

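### For the second primary endpoint, registry cases count up to 2 June 2021 but non-cases are censored at their last report, so the Kaplan-Meier curve will be too high

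*SAP*

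**What the plan says.** SAP 6.1 makes each primary variable a Yes/No value with a time attached, except the third, which is a count. The time is the "time from one week after start of oil consumption to first reporting of the condition". For everyone else, "Those not reporting a Yes answer, the last reported time will be used as censoring time". No separate rule is given for outcomes taken from a registry.

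The second primary is such an outcome: "Second primary: COVID-19 defined by positive PCR obtained from MSIS". SAP Appendix 1 restricts it to tests in the participation period, "defined as period from start of cod liver oil/placebo consumption (*deriv_Date_CLO_start_corr*) to June 2, 2021". Form return plays no part in that window. Section 8 of the protocol states the general principle: "Endpoint ascertainment will be done by obtaining endpoint data from relevant registries". Its section 7 treats a participant as lost only when, among other things, registry data are no longer recorded, which it expects mainly through moves abroad.

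The time-to-event analyses are named in both documents. Protocol section 9, Analysis sets, says "The primary endpoints will be calculated using relative risks, Kaplan-Meier plots and Cox regression" in the ITT population. SAP 6.2 plans Kaplan-Meier plots for the primary variables, and Cox regression if appropriate. The confirmatory analysis in SAP 6.2 is a risk ratio with a Wald test, and SAP 4.1 places regression outside the fallback procedure.

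**The concern.** Take two participants who return their last form in January. One tests positive in April and enters the analysis as an April event, having been at risk until then. The other never tests positive and leaves the risk set in January, although MSIS would have shown a positive test at any time up to 2 June. How long a person stays under observation therefore depends on whether they become a case. Kaplan-Meier and Cox methods both assume that it does not.

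At stake is the published absolute risk of COVID-19 by arm, which would disagree with the trial's own risk ratio table, because that table keeps all non-cases in the denominator. If form return differed between arms, the hazard ratio for treatment would also move.

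**Working it through.** **The plan's own figure.** For the second primary, SAP 3.3 gives 1% incidence, a 20% reduction, alpha 0.03, 70% power and 65,000 participants. With p1 = 0.010, p2 = 0.008 and mean 0.009, two-sided:

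n per arm = [2.170 × √(2 × 0.009 × 0.991) + 0.524 × √(0.010 × 0.990 + 0.008 × 0.992)]² / 0.002² ≈ 32,377, or 64,754 in total.

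This agrees with 65,000. The same method gives 66,684 for the first primary, against 67,000 stated. The 1% risk and the ratio 0.80 are therefore used below, with 32,500 per arm.

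**Assumptions not in the documents.** 180 days of follow-up, constant hazard, monthly forms (the protocol's schedule), and the share who stop returning them. Stopping is spread evenly over months 1 to 5.

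**Kaplan-Meier curve, equal return in both arms.** Let G be the share of non-cases still followed in each of the six months. Because cases are few, the curve ends at about the true risk × the mean of 1/G.

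- 20% stop: G = 1, 0.96, 0.92, 0.88, 0.84, 0.80. The sum of 1/G is 6.705, and 6.705 / 6 = 1.118, so a true 1.00% reads 1.12%.
- 30% stop: G = 1, 0.94, 0.88, 0.82, 0.76, 0.70. The sum of 1/G is 7.164, and 7.164 / 6 = 1.194, so it reads 1.19%.
- 10% and 50% stop: large-sample results are 1.05% and 1.40%.
- 20% or 30% never report and get zero follow-up unless they are cases: 0.01 / (0.01 + 0.99 × 0.80) = 1.25%, or 0.01 / (0.01 + 0.99 × 0.70) = 1.42%.

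**Cox treatment ratio.** The planned rule multiplies it by roughly the mean over months of G(placebo) / G(oil).

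- Equal return, 0% to 30% stopping in both arms: the factor is 1. The large-sample ratio stays at 1.00 under no effect and 0.80 under a true 0.80.
- 20% placebo, 30% oil: the monthly ratios are 1, 1.021, 1.045, 1.073, 1.105 and 1.143, with mean 1.065. The large-sample Cox limit is 1.063 under no effect, and a true 0.80 reads 0.85.
- 30% placebo, 20% oil: the mean is 0.941. A true 1.00 reads 0.94, and a true 0.80 reads 0.75.
- A 5-point gap (20% against 25%): a true 1.00 reads 1.03 or 0.97, depending on which arm returns fewer forms.

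In the 20% against 30% case, a Cox test at nominal 3% would reject a true null 8.4% of the time. With 30% stopping on oil and a true 0.80, its power would be 42% instead of 70%. A simulation agreed with these limits to within Monte Carlo error.

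**Covariates.** The same argument applies to any baseline variable in the SAP 6.2 list. If it predicts form return, its hazard ratio shifts even when the arms are balanced.

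**After the change.** With second-primary non-cases followed to 2 June 2021, the curve ends at 1.00% and the hazard ratio is 0.80 at any level of form return. The Wald risk ratio is the same in every scenario, because it uses no censoring time.

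**The case against.** The strongest objection concerns the wording. The last reported time is not defined, and SAP 6.1 also uses the language of reporting for variables derived from MSIS. If it meant the registry cut-off, nothing would be wrong. That reading is possible but less natural. The rule speaks of people who do not report a Yes answer, and SAP 5.4 ties similar words to data collection: "The number of participants with last reported data will be presented for each data collection time-point". The conclusion rests on the questionnaire reading, and on either reading the term needs a definition.

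A second objection is that only supportive analyses are involved. This stands. In the SAP, Kaplan-Meier is a plot and Cox is conditional. Treatment is not in the list of Cox explanatory variables, and the fallback, logistic regression, has no censoring. The protocol nevertheless names both time-to-event methods for the primary endpoints.

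A reader might extend the point to the first primary, since it also starts from an MSIS-positive test. The documents do not support that. Appendix 1 takes dyspnoea and hospitalisation from forms submitted after the positive test, so someone who has stopped returning forms cannot become a non-fatal event. Events and censoring largely share a source. Following non-cases to 2 June would do harm there. Mean G is 0.90 with 20% stopping and 0.85 with 30%, so about 10% to 15% of non-fatal events would be missed while the person-time still counted. With 30% stopping on oil and 20% on placebo, a true ratio of 1.00 would read 0.85 / 0.90 = 0.94.

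A reader might also infer that the hazard ratio for treatment is biased as planned. That requires unequal form return. The trial is masked and placebo-controlled, and nothing in the documents indicates unequal return.

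Finally, the scenario in which some never report is the least secure, because the documents do not say what start date such a person would have.

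**Conclusion.** Wrong as written for the second primary, with low to moderate severity. On the questionnaire reading, the Kaplan-Meier curve overstates cumulative risk without any imbalance between arms: by about 12% to 19% in relative terms if 20% to 30% stop reporting early, and by more if some never report. The Cox treatment ratio moves only with unequal return, towards or away from benefit, by about 6% for a 10-point gap. These sizes depend on assumed return rates, constant hazard and 180 days. The direction of the Kaplan-Meier error does not depend on those values, provided some non-cases stop reporting before 2 June.

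It would go too far to conclude that the trial's confirmatory result is compromised. The censoring rule does not enter the risk ratio, its alpha or the sample size. The third primary has no event time, and last-report censoring suits the self-reported fourth.

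**What to change.** In SAP 6.1, state that for the second primary only, participants without an event are censored at the earliest of 2 June 2021, death, emigration or withdrawal of consent to registry data. Define the last reported time as the date of the last returned questionnaire and keep it for the fourth primary. State the first primary's rule separately, and do not move it to 2 June while its non-fatal events depend on forms.

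The cost is a short text change and one derived variable. No new outcome data are needed, and the sample size, testing order and alpha stay as they are. Deaths are already taken from the National Population Register (Appendix 1). The protocol lists the population register for address data, so the sponsor should confirm that emigration dates can be obtained from it.
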